- Have previously participated in this same study.
- Be a user of contact lenses and can not suspend their use during the study.
- That they can not follow the lifestyle considerations described in section 6.2.2
- Having started the use of hormonal contraceptives or IUD, 30 days prior to inclusion in the present study.
- Having a history of any chronic-degenerative disease.
- Present inflammatory or infectious disease, active at the time of admission to the study.
- Present injuries or unresolved traumas at the time of entering the study.
- Having the antecedent of any type of eye surgery.
- Having undergone surgical procedures, not ophthalmological, in the last 3 months.

Test product, dose and route of administration:

- PRO-179. Travoprost 0.004%. Ophthalmic solution. Sophia Laboratories, S.A. of C.V.
- Dosage: 1 drop at night.
- Route of administration: Ophthalmic.

Reference product, dose and route of administration:

- Travatan®. Travoprost 0.004%. Ophthalmic solution. Alcon Laboratories, Inc.
- Dosage: 1 drop at night. Both eyes.
- Route of administration: Ophthalmic.

Treatment duration:

10 days.

Duration of subject in the study:

15 to 22 days.

Evaluation criteria:

Primary outcome variables:

- Incidence of adverse events (AD) (Evaluation Time: day 5, 11 and 14).
- Ocular Comfort Index Score (ICO) (TE: day 11).

Secondary outcome variables:

- Changes in visual ability (TE: day 5 and 11).
- Changes in corneal and conjunctival staining with lysine green (TE: day 5 and 11).

- Changes in corneal and conjunctival staining with fluorescein (TE: day 5 and 11).
- Changes or conjunctival hyperemia (TE: day 5 and 11).
- Incidence of chemosis (TE: day 5 and 11).
- Incidence of alterations in the results of laboratory tests (TE: day 11).
- Incidence of alterations in heart rate (HR) (TE: day 5 and 11).
- Incidence of alterations in the respiratory frequency (RR) (TE: day 5 and 11).
- Incidence of alterations in systemic blood pressure (SBP) (TE: day 5 and 11)).

[figure not shown]
Exploratory outcome variables:

- Changes in intraocular pressure (TE: day 5 and 11).

Statistical methodology:

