- Compare the safety of PRO-179 with Travatan® by the incidence of chemosis during visits.
- Compare the safety of PRO-179 with Travatan® by means of the incidence of alterations in the results of the laboratory tests on day 11.

- Compare the safety of PRO-179 with Travatan® through the incidence of changes in HR during visits.
- Compare the safety of PRO-179 with Travatan® by means of the incidence of RF alterations during visits.
- Compare the safety of PRO-179 with Travatan® by the incidence of changes in SAD during visits.

5.5.3 Exploratory objectives.

- Compare changes in intraocular pressure during visits.

5.5.4 Hypothesis.

H0 The ophthalmic solution PRO-179 presents a profile of safety and tolerability similar to Travatan® in healthy subjects.

Ha The ophthalmic solution PRO-179 presents a different safety and tolerability profile Travatan® in healthy subjects.

5.6 Design and plan of the study.

Clinical trial, phase I, controlled, of parallel groups, double blind with randomization.

5.6.1 Discussion of the study design.

The design of the study (clinical trial) is considered the highest standard of data quality when looking to explore the effect of an intervention. The phase of pharmacological development (phase I) corresponds to the objective of the study which is to assess safety and tolerability, so that the intervention time is short and the sample size required is less than that of a clinical efficacy trial. The presence of parallel groups allows the comparison between the intervention groups on the outcome variables. Blinding and randomisation allow to reduce biases that are incurred with other designs, eg. selection bias, evaluation bias, among others.

The comparator, Travatan®, has a known safety profile and shares the same active principles in the same concentrations as PRO-179, which is why it was chosen as the best option to compare.

5.6.2 Justification of the posology.

The chosen dosage is one drop every 24 hours at night, this is the indicated and approved dosage for the reference medicine. Clinical studies demonstrate the sufficiency of 1 drop every 24 hours; likewise, they have shown that the administration at night presents less IOP fluctuations during 24 hours, unlike the morning application. [38]

For this phase I study, we do not consider it necessary to expose the research subjects to dosage rates higher than those recommended, since it is not justifiable.

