The return will be made by the research center when the sponsor indicates it. Prior to the return, the research center must make a count of the assigned medication and the remaining medication, with the aim of creating an inventory which serves for the final filling of the medication return form.

6.4 Delay variables.

6.4.1 Security variables.

6.4.1.1 Primary outcome variables.

- Incidence of adverse events.

6.4.1.2 Variables of primary outcome of tolerability.

- ICO score.

6.4.1.3 Secondary outcome variables.

- Changes in visual ability.
- Changes in corneal and conjunctival staining with lysine green.
- Changes in corneal and conjunctival staining with fluorescein.
- Changes conjunctival hyperemia.
- Incidence of chemosis.
- Incidence of alterations in the results of laboratory tests.
- Incidence of alterations in the FC.
- Incidence of alterations in the RF.
- Incidence of alterations in the TAS.

6.4.2 Exploratory variables.

- Changes in IOP.

6.4.3 Methods and scales to be used for the measurement of the variables.

Variable	Kind	Unit (Symbol)	Method of measurement	Normal value	Evaluation time	Statistical test
Primary						
Adverse events	Discreet Categorical rating	Number of cases (n) Present/absent	Count Observation	0 Absent	VB, V1, VF y LLS	Mann-Whitney U χ^2 o Fisher's exact
ICO score	Discreet	Points	Questionnaire	NA	VB, VF	Mann-Whitney U
Secondary						
Visual ability	Discreet	Fraction	Snellen Primer	1	VB, V1 y VF	Mann-Whitney U
Corneal and conjunctival staining with fluorescein	Ordinal	Degrees	Direct observation with slit lamp and cobalt blue filter, Oxford scale graduation	0	VB, V1 y VF	χ^2 or Fisher's exact

Variable	Kind	Unit (Symbol)	Method of measurement	Normal value	Evaluation time	Statistical test
Corneal and conjunctival staining with lysamine green	Ordinal	degrees	Direct observation with slit lamp, Oxford scale graduation	0	VB, V1 y VF	χ^2 or Fisher's exact
Conjunctival hyperemia	Ordinal	Normal / Very Light / Mild / Moderate / Severe	Direct observation. Classification of Efron.	Normal	VB, V1 y VF	χ^2 or Fisher's exact
Chemosis	Categorical rating	Present / absent		Absent	VB, V1 y VF	χ^2 or Fisher's exact
FC	Discreet	eats per minute (l / m)	Auscultation with stethoscope	60 to 100	VB, V1 y VF	Mann-Whitney U
FR	Discreet	Breaths per minute (r / m)	Auscultation with stethoscope	12 to 24	VB, V1 y VF	Mann-Whitney U
TAS	Discreet	Millimeters of mercury (mmHg)	Measurement with sphygmomanometer	90-120/ 60-80	VB, V1 y VF	Mann-Whitney U

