Erythrocytes	Continuous	Thousands per microliter (Mil / dL)	Laboratory analysis	4.0- 6.3	VB y VF	Mann-Whitney U
Hemoglobin	Continuous	Grams over deciliter (g / dL)	Laboratory analysis	11.0-16.0	VB y VF	Mann-Whitney U
Hematocrit	Continuous	Percentaje (%)	Laboratory analysis	36-51	VB y VF	Mann-Whitney U
VGM	Continuous	Femto liters (fL)	Laboratory analysis	80-97	VB y VF	Mann-Whitney U
HCM	Continuous	Picograms (pg)	Laboratory analysis	25-32	VB y VF	Mann-Whitney U
Leukocytes	Continuous	Thousands per liter units (Mil / uL)	Laboratory analysis	4.0-11.0	VB y VF	Mann-Whitney U
Platelets	Continuous	Thousands per liter units (Mil / uL)	Laboratory analysis	150-400	VB y VF	Mann-Whitney U
Glucose	Continuous	Milligrams over deciliter (mg / dL)	Laboratory analysis	70-100	VB y VF	Mann-Whitney U
Urea	Continuous	Milligrams over deciliter (mg / dL)	Laboratory analysis	10-50	VB y VF	Mann-Whitney U

Variable	Kind	Unit (Symbol)	Method of measurement	Normal value	Evaluation time	Statistical test
Creatinine	Continuous	Milligrams over deciliter (mg / dL)	Laboratory analysis	0.6-1.1	VB y VF	Mann-Whitney U
Glutamic pyruvic transaminase	Continuous	Units over liter (U / L)	Laboratory analysis	0-31	VB y VF	Mann-Whitney U
Oxalacetic glutamic transaminase	Continuous	Units over liter (U / L)	Laboratory analysis	0-32	VB y VF	Mann-Whitney U
Total bilirubin	Continuous	Milligrams over deciliter (mg / dL)	Laboratory analysis	0-1.1	VB y VF	Mann-Whitney U
Direct bilirubin	Continuous	Milligrams over deciliter (mg / dL)	Laboratory analysis	0.0-0.3	VB y VF	Mann-Whitney U
Indirect Bilirubin	Continuous	Milligrams over deciliter (mg / dL)	Laboratory analysis	0.0-0.8	VB y VF	Mann-Whitney U
Exploratoria						
Presión intraocular	Continuous	Millimeters of mercury (mmHg)	Goldmann Tonometry	10 to 21	VB, V1 y VF	Mann-Whitney U

Table 3. Table of operational definitions of variables.

The following describes the methods and scales that will be used to measure the variables, which are in strict alphabetical order:

6.4.3.1 Visual capacity.

Visual acuity (VA) is a test of visual function. Spatial visual acuity is the ability to distinguish separate elements of an object and identify them as a whole. It is quantified as the minimum separation angle (located at the nodal point of the eye) between two objects that allows perceiving them as separate objects.

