- Intra-group analysis: will be determined by the Wilcoxon rank test, for quantitative variables [65]
- Inter-group analysis: will be determined by the Mann-Whitney U test Kruskal-Wallis. This non-parametric test will be used to test whether a group of data comes from the same

population. Intuitively, it is identical to the ANOVA with the data replaced by categories using the student's t statistic.

The level of difference to consider significance will be an alpha of 0.05 or less.

The result of nominal and ordinal qualitative variables will be presented in frequencies, proportions and percentages, see table 3 (section 6.4.3).

The statistical analysis to identify significant differences of the qualitative variables will be done creating 2x2 contingency tables and it will be done in the following way:

- Intra-group difference: McNemar test [66]. Which is applied to 2×2 contingency tables with a dichotomous trait, with pairs of matched subjects, to determine if the marginal frequencies of row and column are equal (marginal homogeneity).
- Inter-group difference: Pearson's χ^2 test (or Fisher's exact).

The level of difference to consider significance will be an alpha of 0.05 or less.

For the reporting of adverse events all eyes of those participants who were randomly assigned to an intervention group after the baseline visit will be considered. The results will be expressed in number of cases (eyes).

The final report of the results will be shown in tables or graphs, as appropriate.

It will be considered that the investigational drug is safe and tolerable when there are no clinical and statistical differences in all the variables of primary outcome, with respect to its comparators.

Those subjects who comply with an adherence greater than 60% will be included in the statistical analysis to meet the objective of the study, taken from the subject's diary. It was considered that from the minimum dose necessary to obtain a pharmacological effect (hypotensive / 1 application per day) and the presence of adverse events (exposure) is sufficient to meet the overall design objective, according to the pharmacological characteristics of the IP.

8.3.2 Additional analyzes.

No additional analyzes are contemplated to those previously described. Nevertheless, these may be performed if during the conduction of the study it is required to analyze specific safety aspects of any intervention, maintaining the blinding until the end of the study.

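### The primary day-11 ICO score is compared between arms without the baseline ICO already collected, which gives up precision with 12 subjects per arm

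*Combined protocol and SAP*

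**What the plan says.** - **ICO, primary.** The Synopsis gives the outcome as "Ocular Comfort Index Score (ICO) (TE: day 11", that is, a score on one day and not a change. Table 3 (section 6.4.3) has the row "ICO score Discreet Points Questionnaire NA VB, VF Mann-Whitney U", so the questionnaire is completed at the baseline and final visits and the test is Mann-Whitney. The schedules in 1.3 and 6.5 also place the ICO at the baseline visit.
- **IOP, exploratory.** Section 5.5.3 sets the objective "Compare changes in intraocular pressure during visits" and the Synopsis lists "Changes in intraocular pressure (TE: day 5 and 11". Table 3 has "Goldmann Tonometry 10 to 21 VB, V1 y VF Mann-Whitney U". Baseline IOP may come from screening or from day 1, at the investigator's choice (6.5.1.2).
- **General rule.** Section 8.3.1 states for quantitative variables: "Inter-group analysis: will be determined by the Mann-Whitney U test Kruskal-Wallis". No covariate is named. The only test described that pairs a subject's own values over time is the within-arm Wilcoxon test, which does not compare arms. Section 8.3.2 plans nothing further, except where a specific safety question arises.
- **Decision rule.** Section 8.3.1 regards the product as safe and tolerable if the primary outcome variables show no clinical and statistical difference from the comparator.
- **Size.** Section 6.6.1 settles on 12 subjects per arm.

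**The concern.** A baseline measurement of the same quantity is usually the best available predictor of the final one. Using it as a covariate removes between-subject variation from the arm comparison and needs no new data. The plan collects baseline ICO but does not use it between arms when the day-11 score is tested.

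This matters more than usual because of the decision rule. When tolerability is concluded from the absence of a difference, a noisier comparison makes that conclusion easier to reach. A Mann-Whitney p-value also does not show how large a difference in ICO points has been excluded, whereas an adjusted difference with an interval does.

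For IOP the stake is lower: it is exploratory, no decision rests on it, and it is defined as a change.

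**Working it through.** **1. The plan's own figure.** There is none to reproduce. The documents give no power or precision for ICO or IOP; section 6.6.1 bases the sample size on conjunctival hyperemia.

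**2. Inputs.** N = 24 (12 per arm, section 6.6.1). The baseline-to-follow-up correlation r is an assumption, because the documents do not state it. One value per subject and equal SDs at baseline and follow-up are also assumed.

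**3. Formulas.** Variance of the arm difference, relative to comparing final values:
- final value: 1
- change: 2(1 − r)
- ANCOVA: (1 − r²) × (1 + 1/(N − 4)) = (1 − r²) × (1 + 1/20) = 1.05 × (1 − r²)

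The factor 1.05 is the small-sample cost of estimating the slope. Equivalent subjects per arm, against final values, is 12 divided by the ANCOVA variance.

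| r | Change | ANCOVA | ANCOVA ÷ change | Equivalent n per arm (vs final value) |
|---|---|---|---|---|
| 0.2 | 1.60 | 1.008 | 0.63 | 11.9 |
| 0.3 | 1.40 | 0.956 | 0.68 | 12.6 |
| 0.5 | 1.00 | 0.788 | 0.79 | 15.2 |
| 0.7 | 0.60 | 0.536 | 0.89 | 22.4 |
| 0.8 | 0.40 | 0.378 | 0.945 | 31.7 |
| 0.9 | 0.20 | 0.1995 | 0.9975 | 60.2 |

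**4. Reading the table.** Against final values the cut is 1 − 0.788 = 21% at r = 0.5, 1 − 0.536 = 46% at 0.7 and 1 − 0.378 = 62% at 0.8. Against change it is 21% at 0.5, 11% at 0.7, 5.5% at 0.8 and essentially nil at 0.9.

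**5. Break-even points.**
- Against final values: 1.05(1 − r²) = 1 gives r² = 1 − 1/1.05 = 0.048, so r ≈ 0.22. Below that, adjustment costs a little precision.
- Against change: 1.05(1 + r)/2 = 1 gives r ≈ 0.90.

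**6. Check by simulation.** 4,000 runs, 12 per arm, normal data, true difference 1 SD, two-sided 0.05. Power:

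| r | Mann-Whitney, final value | Mann-Whitney, change | Rank ANCOVA | ANCOVA |
|---|---|---|---|---|
| 0.2 | 61% | 43% | 62% | 64% |
| 0.5 | 62% | 61% | 73% | 76% |
| 0.7 | 60% | 83% | 85% | 89% |
| 0.8 | 62% | 95% | 93% | 97% |

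With no true difference, all four methods rejected in about 4% to 6% of runs. Part of ANCOVA's lead over Mann-Whitney comes from using a parametric test on normal data. The rank ANCOVA column is the fairer measure of what baseline itself adds.

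**The case against.** The planned test is valid. Its type I error is controlled, and an unadjusted rank test is an ordinary choice in a 24-subject phase I study. The size of the gain rests on a correlation with no source in the documents, and r could be low. Healthy subjects with no active inflammatory disease may score close to zero on a 0–100 scale, leaving baseline little to predict. A linear model on a bounded score with 12 per arm has its own assumptions. The variance formulas describe linear estimators, not rank tests, and at r = 0.8 rank ANCOVA did slightly worse than Mann-Whitney on change (93% against 95%).

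All of this stands as a limit on size. It makes a rank-based check necessary. It does not remove the point for ICO, because adjustment costs very little when r is low and gains materially when r is moderate.

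A reader might infer something stronger for IOP: that its comparison ignores baseline, so chance imbalance passes straight into the day-5 and day-11 results. The documents do not support that. The Synopsis, 5.5.3 and 6.4.2 all define the variable as a change, and the visits in the Table 3 row are evaluation times, not a statement that raw visit values are tested. The 21% to 62% range should therefore not be applied to IOP if change is tested. Nor does the no-difference rule reach IOP, since it covers primary outcomes only.

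**Conclusion.** The point holds for the primary ICO score as a low-cost improvement; it does not make the planned test invalid. As written, the day-11 comparison leaves baseline ICO unused, and under the section 8.3.1 rule the resulting imprecision works towards a finding of tolerability. The benefit is material if r is 0.5 or more, small around 0.3 and absent below about 0.22.

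For IOP the issue is the same in kind but smaller. Baseline is probably already partly used through the change, so the remaining gain falls quickly as r rises. What is missing there is a statement of whether change or the visit value is tested.

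These sizes assume 24 analysed subjects. Fewer would raise the small-sample factor slightly; with 20 it would be 1 + 1/16 = 1.0625.

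**What to change.** In Table 3 and section 8.3.1:

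1. Compare day-11 ICO between arms by ANCOVA with baseline ICO as covariate, and report the adjusted difference with its 95% interval.
2. Add rank ANCOVA, or Mann-Whitney on the change, as a sensitivity analysis, because scores may be bounded near zero.
3. Do the same for day-5 and day-11 IOP, using one value per subject (mean of both eyes). Say which baseline reading is used when both screening and day-1 values exist.
4. For every quantitative variable, state whether the between-arm test is run on the change or on the visit value.

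The cost is a few lines of text and one simple model per comparison, with no new data. The statistical price is one degree of freedom and a linearity assumption, which the rank-based analysis checks.

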The data will be expressed with measures of central tendency: mean and standard deviation for the quantitative variables. The qualitative variables will be presented in frequencies and percentages. The statistical analysis will be carried out by means of the Mann-Whitney U test for the quantitative variables for the difference between the groups. The difference between the qualitative variables will be analyzed by means of χ^2 (Chi2) or Fisher's exact. An alpha ≤ 0.05 will be considered significant.

1.2 Diagram of the study.

* Baseline measurements can be taken from those made during the screening visit. It is the investigator's prerogative to perform them again at the baseline visit.

1.3 Schedule of the study .

Procedures	Scrutiny D 1 - X ^a	VB D 1	V1 D 5 ± 1	VF D 11 a + 1	LIS D 14 ± 1
CI Signature	X				
Clinic history	X				
Concomitant Medication Evaluation	X	X	X	X	
Urine pregnancy test	X			X	
Vital signs	X	X ¹	X	X	
CV	X	X ¹	X	X	
Integrity of the ocular surface	X	X ¹	X	X	
PIO	X	X ¹	X	X	
Comprehensive ophthalmological evaluation	X	X ^{1,2}	X	X ²	
Eligibility criteria	X	X ^b			
Blood sampling	X			X	
EA evaluation	X	X	X	X	X
Review of laboratory results		X			X
Assignment of Research Product (PI)		X			
Ocular Comfort Index		X		X	
Delivery of the IP and start of intervention		X			
Adherence evaluation			X	X	
Daily delivery of the subject		X	X		
Continuity evaluation of the subject			X		
Return / Evaluation of the subject's Journal			X	X	
Return of IP				X	

- a. The counting visit may be up to 7 days before the baseline, if it exceeds these the subject can not enter.
- b. These criteria will be completed with the results of the laboratory tests and those obtained during the screening visit. 1 They can be taken from the scrutiny visit, it is the prerogative of the PI to measure them again at the baseline visit. 2 Includes subsequent segment valuation.

**Page intentionally left
blank**

2 Content

1.1 SUMMARY	1
1.2 SYNOPSIS	1
1.2 DIAGRAM OF THE STUDY.	4
1.3 SCHEDULE OF THE STUDY .	5
2 CONTENT	7
3 INDEX OF ABBREVIATIONS.	11
4 ADMINISTRATIVE STRUCTURE OF THE STUDY.	13
5 INTRODUCTION	15
5.1 THEORETICAL FRAMEWORK.	15
5.2 BACKGROUND .	15
5.2.1 PHARMACOLOGY OF TRAVOPROST.	15
5.2.1.1 Pharmacokinetics .	16
5.2.1.2 Pharmacodynamics .	16
5.2.2 EFFICIENCY OF TRAVOPROST.	16
5.2.3 SAFETY OF TRAVOPROST.	17
5.2.4 RISK BENEFIT EVALUATION.	17
5.2.4.1 Known potential risks.	17
5.2.4.2 Known potential benefits.	17
5.3 STATEMENT OF THE PROBLEM.	17

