The closing of the center will be carried out once the last visit of the last included subject previously agreed between the sponsor and the PI has been made. The closing process will be according to the normal procedures of the sponsor's internal operations and must have the disposition and participation of the PI and whoever he designates.

It is the sponsor's prerogative to prematurely close a study center, it must inform the PI the reasons for the closure. These can be, but do not exclude:

- a) Lower recruitment to the projected.
- b) Deviations greater than the protocol, which at the sponsor's discretion merit closing the center.
- c) Recidivism of deviations to the protocol, which at the sponsor's discretion merit closing the center.
- d) Early termination of the study.

6.2 Study population.

6.2.1 Selection criteria.

6.2.1.1 *Inclusion criteria.*

- Be clinically healthy.
- Have the ability to give their signed informed consent and show willingness to comply with the study procedures
- Have an age between 18 to 45 years.
- Indistinct sex.
- Women should ensure the continued use of a hormonal contraceptive method or intrauterine device (IUD) during the study period.
- Present blood tests: within normal parameters or with a range of \pm 20% as long as the subject is clinically healthy.
 - o Blood count (BH): Hemoglobin, erythrocytes, hematocrit, total leukocytes, platelets, mean corpuscular volume and mean corpuscular hemoglobin.
 - o Blood chemistry of three elements (QS): Glucose, urea and creatinine.
 - o Liver function tests (PFH): TGO, TGP, total bilirubin, direct and indirect.
- Present visual ability 20/30 or better in both eyes.
- Present vital signs within normal parameters.
- Present intraocular pressure \geq 10 and \leq 21 mmHg.

6.2.1.2 *Exclusion criteria.*

6.2.1.2.1 General criteria.

- Be a user of ophthalmic topical products of any kind.
- Be a user of medicines, or herbal products, by any other route of administration, with the exception of hormonal contraceptives in the case of women.
- In case of being a woman, being pregnant or breastfeeding.

- Have participated in clinical research studies 90 days prior to inclusion in the present study.
- Have previously participated in this same study.
- Be a user of contact lenses and can not suspend their use during the study.
- That they can not follow the lifestyle considerations described in numeral 6.2.2

6.2.1.2.2. Medical and therapeutic criteria.

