- Urine pregnancy test: Refers to the performance of a rapid pregnancy test in all women of childbearing age who wish to enter the study. By fertile age we understand women who have presented their menarche and have not presented their menopause. Menopause is defined as 12 months from the last menstruation in women over 40 years of age; or those who underwent bilateral hysterectomy or oophorectomy. Women of childbearing age with contraceptive methods including bilateral tubal obstruction should be tested for pregnancy. This test will be done by the PI or the designated team person according to the instructions of the device delivered by the sponsor.
- Vital signs: see 6.4.3.7 Vital signs.
- Visual capacity: see 6.4.3.1 Visual capacity.
- Comprehensive ophthalmological evaluation: see 6.4.3.2 Comprehensive ophthalmological evaluation.
- Integrity of the ocular surface: see 6.4.3.4 Integrity of ocular surface:
- Intraocular pressure: see 6.4.3.6 Intraocular pressure.
- Eligibility criteria: refers to the review by the PI, where it states that the subject can be included in the study by meeting the inclusion criteria and not meeting the exclusion criteria. See 6.2.1 Selection criteria.
- Sampling of laboratory samples: see 6.4.3.8 Laboratory tests.
- Adverse events: see 6.4.3.5 Presence of adverse events.

6.5.1.2 Basal visit.

- Review of laboratory tests: refers to the review and analysis by the PI of the results of the BH, QS and PFH.
- Eligibility criteria: with the results of the laboratory the profile of the subject will end for its inclusion or not.
- Evaluation of variables: The data of the evaluation of the variables listed below can be taken from the scrutiny visit. It is the prerogative of the PI to decide whether to use the information from the screening visit or to repeat the evaluations in this visit.
 - Intraocular pressure
 - Visual capacity
 - Integrity of the ocular surface

- Comprehensive ophthalmologic evaluation
- vital signs
- Eye comfort index: see 6.4.3.3 Eye comfort index.
- Assignment of IP: Refers to determine the intervention that the patient will follow during the study. It will be done according to the Methods section. Assignment of the intervention. This assignment will be made at the baseline visit (day 1) and will go along with the indication to start the treatment period at night.

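### Reusing the qualifying screening vital signs as baseline can bias the within-arm before/after tests, mainly for blood pressure

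*Combined protocol and SAP*

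**What the plan says.** **Entry.** Section 6.2.1.1 (and the synopsis) requires each subject to "Present vital signs within normal parameters". It gives no limits. The only numeric ranges for vital signs are in the normal-value column of Table 3 (section 6.4.3): heart rate 60 to 100, respiratory rate 12 to 24, blood pressure 90-120/60-80.

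**Baseline.** The note to the study diagram says "Baseline measurements can be taken from those made during the screening visit". Section 6.5.1.2 repeats this for a list that includes vital signs: "The data of the evaluation of the variables listed below can be taken from the scrutiny visit". It leaves the choice open: "It is the prerogative of the PI to decide whether to use the information from the screening visit or to repeat the evaluations". On eligibility, note b to the schedule says "These criteria will be completed with the results of the laboratory tests and those obtained during the screening visit".

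**Outcomes.** The incidence of alterations in heart rate, respiratory rate and blood pressure at days 5 and 11 is a secondary outcome. The matching objectives in section 5.5.2 compare the two products, for example "through the incidence of changes in HR during visits". Table 3 lists the same variables as numeric, compared between arms by Mann-Whitney U.

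**Within-arm tests.** Section 8.3.1 plans, at alpha 0.05, "Intra-group analysis: will be determined by the Wilcoxon rank test, for quantitative variables". For qualitative variables it plans McNemar on 2x2 tables. Vital signs are not exempted from either.

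**The concern.** A reading that had to be normal for the subject to enter is not a neutral starting point. If it also serves as the baseline, and an alteration means falling outside the same range, nobody is altered at baseline. Every discordant McNemar pair is then a worsening, and the marginal homogeneity that McNemar tests fails before any drop is given.

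The numeric values have a related problem. Where the range cuts more off one side of the population than the other, follow-up values regress toward the uncut mean. A ceiling of 120/80 may do this to blood pressure in healthy adults.

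At stake is a within-arm result reported as a significant blood-pressure change when neither product has any effect. In a trial run to document a safety profile, that would be a false signal in a secondary variable.

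**Working it through.** The plan gives no figure on this point to reproduce. From the documents come 12 subjects per arm (section 6.6), the Table 3 ranges and alpha 0.05, taken as two-sided. They give no population means or variances for vital signs, so those below are assumptions.

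**1. McNemar threshold.** With zero altered at baseline and b altered at follow-up, the exact two-sided p is 2 × 0.5^b.
- b = 5: 2 × 0.03125 = 0.0625.
- b = 6: 2 × 0.015625 = 0.031.

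Six altered subjects of 12 are therefore enough. The plan does not say which version of McNemar is meant. The uncorrected chi-square version, (4 − 0)²/4 = 4, already gives p = 0.046 at b = 4, so the exact figures below are the cautious ones.

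**2. Blood pressure with no drug effect.** Each simulated subject has a true systolic/diastolic level plus independent visit-to-visit variation. Subjects are selected on one reading inside 90-120/60-80 and then re-measured. Assumed ranges, low to high:
- systolic mean 112-118, between-person SD 8-10, visit-to-visit SD 5-8;
- diastolic mean 71-75, between-person SD 6-8, visit-to-visit SD 4-6;
- systolic-diastolic correlation 0.6.

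| | Low | Middle | High |
|---|---|---|---|
| Out of range at day 11 | 0.177 | 0.303 | 0.399 |
| P(at least 6 of 12), binomial | 0.011 | 0.122 | 0.333 |
| Apparent systolic rise (mmHg) | 0.7 | 1.8 | 3.1 |
| Wilcoxon on systolic, qualifying reading as baseline | 0.055 | 0.093 | 0.148 |

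The second row is the exact McNemar rejection rate. With a separate day-1 reading as baseline, the expected drift is zero, exact McNemar rejects in under 1% of arms, and Wilcoxon rejects in 4.1-4.3%.

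**3. Other assumptions.** With total SDs of 11 and 8 mmHg, visit-to-visit correlation 0.5 or 0.7 and means of 108-115/68-74, 23-34% are out of range at one visit and exact McNemar rejects in 4-20% of arms.

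Wilcoxon on systolic pressure depends on how close the mean lies to 120. In the step 2 model at 105-110/70 it rejects in 4.3-5.2%. With systolic pressure alone, SD 11 and correlation 0.5-0.85:
- mean 105: 4.1-4.3%;
- mean 110: 4.6-6.2%;
- mean 115: 6.3-11.8%;
- mean 120: 9.4-25%.

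**4. Heart and respiratory rate.** For heart rate (means 68-80, SD 10), 3-15% are out of range at follow-up, exact McNemar rejects in at most 0.4% of arms and Wilcoxon in 4.1-7.5%. The top value occurs at mean 68 with correlation 0.5. For respiratory rate (means 16-18, SD 2.5), 1-5% are out of range, McNemar rejection is essentially zero and Wilcoxon rejects in 4.4-5.0%.

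**5. Between arms.** The same selection applies to both arms. Fisher's exact test with 12 per arm and equal altered rates of 10-45% rejects in 0.2-2.2%, so there is no inflation.

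**The case against.** The strongest reply is that several links are inferred, and that nothing the trial concludes depends on them.

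- **Ranges.** No section ties the entry rule, or the word alteration, to Table 3. For laboratory tests the plan uses the laboratory's ranges with a 20% margin at the investigator's discretion, so a hard Table 3 cut cannot be taken for granted. This stands. Table 3 is nevertheless the only place where a normal blood pressure is given in numbers.
- **Baseline.** A reader might infer that baseline alterations are zero for every subject and that the within-arm null is false by design. The documents do not support that. The investigator may repeat the readings on day 1, and since eligibility draws on the screening results, a repeated baseline can lie outside the range.
- **Test.** Section 8.3.1 assigns McNemar to qualitative variables, whereas Table 3 treats vital signs as numeric. Applying McNemar to alterations follows naturally from the incidence wording but remains an inference, and the largest percentages rest on it.
- **Size.** The Wilcoxon effect is small unless mean systolic pressure is near the ceiling. This stands.
- **Scope.** A reader might extend the problem to all vital signs. Step 4 does not support that beyond a small Wilcoxon effect on heart rate when its mean is near the lower limit.
- **Consequence.** A reader might infer that the comparison of products, or the verdict of safe and tolerable, is compromised. It is not: the vital-sign objectives are between-arm, and the rule in section 8.3.1 uses primary outcomes against the comparator.

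What survives is narrower: the plan permits a biased baseline for a planned test, and choosing it subject by subject can mix biased and unbiased baselines within an arm.

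**Conclusion.** The point holds in a limited, conditional form. Where the screening reading is reused, and if entry normality and alteration both mean the Table 3 ranges, within-arm incidence of alterations can only worsen.

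For blood pressure, under the assumed means of 112-118/71-75 mmHg, a no-effect arm of 12 would show a significant exact McNemar result about 1-33% of the time and a significant Wilcoxon result on systolic pressure about 5-15% of the time. These spans reflect ignorance of the population, not simulation error, and the lowest scenario shows little or no inflation.

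Counting an alteration at either day 5 or day 11 would give larger McNemar rates. The plan does not define the outcome that way, and two follow-up chances against one baseline reading is a separate artefact, so those rates should not be charged to this point. Severity: minor.

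**What to change.** In sections 6.5.1.2 and 8.3.1, make the day-1 pre-dose reading the baseline for vital signs in every subject, separate from the screening reading that decides eligibility. The schedule already allows this measurement. Report within-arm changes in blood pressure descriptively, and rest the secondary vital-sign statement on the between-arm comparison, which is the stated objective. It would also help to say what counts as an alteration and which ranges the entry rule uses, since the size of the problem depends on both; that choice belongs to the sponsor's clinical team.

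The cost is one short pre-dose reading on day 1 for every subject, some wording, and the loss of within-arm p-values for blood pressure. No stated objective needs those p-values.
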